# Causality

The *causal relation* of the AE to the use of the IMP should be described in terms of probably, possibly, or not related according to the investigator's clinical judgement.

Probably related	Follows a reasonable temporal sequence from administration of the IMP.  Could not be reasonably explained by the subject's clinical state, environmental or toxic factors, or other therapies administered to the subject.  Follows a known pattern of response to the IMP.
	Disappears or decreases on cessation or reduction in dose of the IMP.
	Reappears or worsens upon re-challenge.
Possibly related	Follows a reasonable temporal sequence from the administration of the IMP.  Could also be reasonably explained by the subject's clinical state, environmental or toxic
	factors, or other therapies administered to the subject.
	Follows a known pattern of response to the IMP.
Not related	Does not follow a reasonable temporal sequence from administration of the IMP.
	Is better explained by other factors like the subject's clinical state, environmental or toxic factors, or other therapies administered to the subject.
	Does not reappear or worsen upon re-challenge.
	Does not follow a known pattern of response to the IMP.

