#### 5.5 Benefit/risk assessment

#### LEO 138559

No risks have been observed in nonclinical studies or clinical trials with LEO 138559.

According to the results from the FiH (LP0145-1315), single IV doses up to 75 mg, single SC doses up to 300 mg, and multiple SC doses up to 450 mg LEO 138559 are considered safe and well tolerated. No severe or serious AEs were reported in this trial.

The following are considered important potential risks for LEO 138559 based on mechanism of action and class effects of other biologics.

IL-22 has been shown to mediate cutaneous and mucosal host defence in the skin, lung, and intestine and induce expression of epithelial antimicrobial peptides. Therefore, when blocking IL-22R, there is a potential for increased risk of infection. However, based on the data reported in subjects with AD treated with the monoclonal antibody targeting IL-22 (fezakinumab) and the available data from LEO138559, no increased risk of infections has been observed by blocking the IL-22 pathway.

IL-22 is known to play a role in tissue regeneration and wound healing and blocking IL-22R could potentially delay skin, lung, intestine, and pancreas healing. The risk is considered low as many growth factors and cytokines have overlapping roles for tissue regeneration and wound healing.

Immunogenicity is a class effect of mAbs, though the risk of immunogenicity of LEO 138559 is predicted to be lower than current biologics as predicted by the in silico Epibase scanning system [39].

Anaphylaxis and serious allergic reactions have been observed after the administration of mAbs and other foreign proteins. In addition, AD subjects are at an increased risk of hypersensitivity reactions.

However, in the FiH trial, no trends for impaired wound healing, no anaphylaxis or serious allergic reactions were observed.

The FiH trial revealed promising efficacy results in AD patients for the 300 mg and 450 mg treatment groups. Treatment- and dose-related reductions in mean EASI and IGA scores were observed. Reductions from baseline in EASI score  $\geq$ 90% occurred in 3 out of 4 subjects following administration of 450 mg LEO 138559.

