### **Dupixent**®

As comparator dupilumab (Dupixent®) was chosen, a systemic targeted immunomodulatory agent approved for the treatment of moderate-to-severe AD since 2017. Dupilumab is a human monoclonal IgG4 antibody that inhibits interleukin-4 (IL-4) and interleukin-13 (IL-13) signaling by specifically binding to the IL-4R $\alpha$  subunit shared by the IL-4 and IL-13 receptor complexes. Blocking IL-4R $\alpha$  with dupilumab inhibits IL-4 and IL-13 cytokine-induced

Trial ID: LP0145-2274 Date: **04-Jan-2023** 

Page 39 of 129

Version: 5.0

responses, including the release of proinflammatory cytokines, chemokines and IgE and modulated the Type 2 pathway.

Dupixent® will be used in this trial in a dosing scheme as per approved label in Austria.

Side effects are injection site reactions (includes erythema, oedema, pruritus, pain, and swelling), conjunctivitis, arthralgia, oral herpes, and eosinophilia. Rare cases of serum sickness, serum sickness-like reaction, anaphylactic reaction, and ulcerative keratitis have been reported as described in the summary of product characteristics (SmPC) for Dupixent®.

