#### 10.2 Reasons for discontinuation of IMP

### 10.2.1 Reasons for permanent discontinuation of IMP

Subjects will permanently discontinue IMP in the event of:

- Withdrawal by subject
- An AE that, in the opinion of the investigator or sponsor's medical expert, contraindicates further dosing.
- Confirmed clinically significantly abnormal ECG or change in ECG.
- Initiation of prohibited medication which cannot be safely replaced by other non-prohibited medications.
- Evidence of pregnancy, or if the subject is noncompliant with the contraception requirements (see Section 8.2).
- Symptomatic infection with SARS-CoV-2 that is likely to have an impact on efficacy or safety data (i.e., patients with a SARS-CoV-2 infection without or very mild symptoms only (e.g., rhinitis or sore throat) might continue with the study at investigator's discretion and in accordance with the applicable local regulations)..
- Other reasons, at the discretion of the investigator. If other, a specification should be provided.

Page 66 of 129

It is not allowed to restart IMP treatment after discontinuation of IMP.

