## 13.4.2 LEO Pharma reporting responsibilities

Global Safety at LEO Pharma is responsible for assessing whether an SAE is expected. The relevant reference safety information documents for this clinical trial are:

- For the drug product LEO 138559, the investigator's brochure Section 7.3.8, edition 4 and subsequent updates must be used.
- For the comparator Dupixent® the latest version of the SmPC [54] must be used.

Global Safety at LEO Pharma will notify the regulatory authorities and concerned investigators of SAEs according to the current applicable legislation for the concerned country.

The IRB(s)/IEC(s) will be notified of SAEs according to the current applicable legislation for the concerned country.

For all non-US countries, the following reporting requirements apply: all SAEs which are assessed as causally related to the IMP(s) by either the investigator or LEO Pharma [55], and which are unexpected (suspected, unexpected serious adverse reactions [SUSARs]), are subject to expedited reporting to regulatory authorities and IEC(s)/IRB(s) according to the current applicable legislation in the concerned countries. Investigators will be notified of the evolving safety profile of the IMP on an ongoing basis.

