# 13.7 Follow-up for final outcome of adverse events

During the trial, the investigator should follow up for final outcome on all AEs (including SAEs). Once a subject leaves the clinical trial, the investigator should follow up on the outcome of all non-serious AEs classified as possibly or probably related to the IMP for 2 weeks after visit 16 or until the final outcome is determined, whichever comes first. Non-serious AEs classified as not related to the IMP do not need to be followed up for the final outcome.

All SAEs must be followed up until a final outcome has been established, that is, the follow-up may continue beyond the end of the clinical trial. For SAEs which have stabilised and from which the subject cannot be expected to recover during the trial or the safety follow-up periods, e.g. chronic or stabilised conditions, the final outcome at the investigator's discretion should be reported as 'recovering/resolving' or 'not recovered/not resolved'. In addition, a statement detailing why the subject cannot be expected to recover during the trial, e.g. that the SAE has stabilised or is chronic, should be added to the narrative description of the SAE on the SAE form.

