#### 14.3.9.1 Adverse events

AEs will be coded during the course of the trial according to Medical Dictionary for Regulatory Activities (MedDRA). AEs will be presented by preferred term and primary system organ class (SOC).

Treatment-emergent AEs will be summarised; however, all AEs recorded during the course of the trial will be included in subject data listings. The tabulations described in the following will only include the treatment-emergent AEs. In each of the tabulations, AEs are defined by MedDRA preferred terms within primary SOC.

AEs will be summarised in terms of the number of subjects with at least 1 event, the percentage of subjects with at least 1 event, the number of events, and the event rate per 100 patient years of observation time.

Related AEs are defined as AEs for which the investigator has not described the causal relationship to IMP as 'not related'.

An overall summary of the number of events and the number (percentage) of subjects with any treatment-emergent AEs, deaths, SAEs, permanent discontinuations from IMP, and/or withdrawals from the trial due to AEs, treatment-related AEs, mild and moderate AEs, and severe AEs will be presented.

Tabulations by SOC and preferred term will be presented for all AEs, SAEs, related AEs, and AEs leading to withdrawal from trial and/or permanent discontinuation of IMP. In addition, all AEs will be presented by severity and causal relationship to IMP, respectively.

The number of AEs and number of subjects with each type of AEs will be tabulated by treatment group from baseline to week 16, from baseline to week 32, and from week 17 to week 32.

AEs leading to withdrawal from trial and/or permanent discontinuation of IMP will be tabulated and listed. The detailed listing will provide an overview of the individual cases and include the age and sex of the subject, treatment received at the time of AE onset, the AE preferred and reported terms, causality and severity of the AE, the action taken with the IMP, AE outcome, start and stop date of AE, duration of AE, and number of days since first and last IMP administration. No narratives will be given.

SAEs will be evaluated separately, and a narrative will be given.

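### Appendix 2 treats lack of a known response pattern as a mark of an unrelated AE, so a new kind of reaction to LEO 138559 fits no related category

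*Combined protocol and SAP*

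**What the plan says.** **The scale.** Appendix 2 (Causality) has three categories and leaves the choice to the investigator's clinical judgement. Both probably and possibly related include "Follows a known pattern of response to the IMP". Not related includes "Does not follow a known pattern of response to the IMP". Nothing says whether one mark is enough or all are needed.

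**The two products.** Section 5.2 describes LEO 138559 as at an early stage with limited clinical data: 35 subjects exposed and no AE pattern of concern. Section 5.5 states "No risks have been observed in nonclinical studies or clinical trials with LEO 138559" and then names potential risks from mechanism and class. For dupilumab the same section gives a known profile, beginning "Side effects are injection site reactions" and going on to conjunctivitis, arthralgia, oral herpes and eosinophilia.

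**Where the label is used.**
- Section 14.3.9.1: "Related AEs are defined as AEs for which the investigator has not described the causal relationship to IMP" as not related.
- Section 13.4.2: expedited reporting covers "all SAEs which are assessed as causally related to the IMP(s) by either the investigator or LEO Pharma", if also unexpected.
- Section 13.7, on subjects who have left the trial: "Non-serious AEs classified as not related to the IMP do not need to be followed up for the final outcome".

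**The concern.** The secondary objective is the safety of LEO 138559. In an early-stage product the events of most interest are those nobody has yet described. On this scale, being undescribed counts against relatedness, whatever the timing and whether or not another cause is in sight.

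The mark may also work unevenly between the arms. The investigator is blinded and judges each event against a trial product that could be either drug. An event on the dupilumab profile satisfies the pattern mark; an event of a new kind does not. New kinds of event are more plausible with the less studied product, so any tilt in the related-AE comparison would favour LEO 138559. With 8 subjects planned on LEO 138559, a new reaction may appear as a single case, and its label then decides whether it appears in the related-AE table at all.

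**Working it through.** **1. One event against the table.** Take an event that is well timed, has no other reasonable explanation and is of a new kind. De-challenge and re-challenge information is not yet available.

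| Category | Marks met | Marks failed | Marks open |
|---|---|---|---|
| Probably related (5 marks) | timing; no other explanation | known pattern | de-challenge; re-challenge |
| Possibly related (3 marks) | timing | other explanation also reasonable; known pattern | none |
| Not related (4 marks) | no known pattern | implausible timing; better explanation | re-challenge |

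No row fits. Give the same event a known pattern and probably related has three marks met and none failed, while not related has none met. The pattern mark alone makes the difference.

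Now take the commoner case: well timed, new in kind, with another explanation also reasonable. Possibly related would fit on timing and on explanation, and fails only on pattern. The pattern mark therefore acts on the boundary between possibly and not related, which is the boundary that defines a related AE in Section 14.3.9.1.

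**2. Is a first-time reaction realistic?** The protocol gives no design figure to reproduce here, so these are side calculations.

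Prior exposure (Section 5.2): 11 IV and 8 SC single-dose healthy volunteers, plus 12 AD patients and 4 healthy volunteers on multiple doses. 11 + 8 + 12 + 4 = 35, which agrees with the stated total.

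If a reaction was seen in none of n subjects, the one-sided 95% exact upper bound on its rate is 1 − 0.05^(1/n):
- n = 35: 8.2%
- n = 16 (multiple dose): 17.1%
- n = 12 (AD patients): 22.1%

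The chance of at least one case among 8 LEO 138559 subjects is 1 − (1 − p)^8. The true rates p are assumptions:

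| p | Chance of at least one case |
|---|---|
| 1% | 7.7% |
| 2% | 14.9% |
| 5% | 33.7% |
| 10% | 57.0% |

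Earlier exposure leaves room for reactions that are common enough to appear here for the first time.

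**3. What a label of not related changes.**

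| Use | Effect |
|---|---|
| Related-AE tables (14.3.9.1) | Event drops out; the investigator's label is the only input |
| SUSAR causality (13.4.2) | Investigator's route lost; sponsor's route remains |
| Expectedness (13.4.2) | None; the sponsor judges it against the reference safety information |
| Follow-up during the trial (13.7) | None; all AEs are followed |
| Follow-up of SAEs (13.7) | None; followed to final outcome |
| Follow-up of non-serious AEs after exit (13.7) | Lost; related ones are followed for at most 2 weeks after visit 16 |
| TEAE count per subject (14.3.6) | None |
| All-AE, SAE and severity tables; listings (14.3.9.1) | None |

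**The case against.** The strongest reply is that the table cannot be meant literally. If every mark were required, probably related would need a positive re-challenge, and not related would need implausible timing as well as a negative re-challenge. The well-timed, unexplained event would then fail not related too. The workable reading is clinical judgement, and on that reading the event contradicts two of the four marks of not related. This stands, and it limits the claim: the wording leans the investigator but does not bind.

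LEO 138559 is also not wholly without a pattern. Section 5.2 records 17 possibly or probably related events in 8 subjects, with infections in 6 of 35, and Section 5.5 names infection, delayed healing, immunogenicity and hypersensitivity as potential risks. Some reactions could be matched to these. The 17 events do not show that investigators will override the list, because the causality scale used in that trial is not given.

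A reader might infer more than the documents support:

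- *New reactions cannot reach SUSAR reporting.* Either party's causality judgement is enough, and expectedness is assessed by the sponsor's safety function against the reference safety information, not against Appendix 2. The sponsor's own causality criteria are not stated, so the second route is open but its strength is unknown.
- *Follow-up of new reactions is lost.* The loss is confined to non-serious events after the subject leaves the trial.
- *Re-challenge can never be observed.* Section 10.2.1 says "It is not allowed to restart IMP treatment after discontinuation of IMP", but that concerns permanent discontinuation. Subjects who continue are re-dosed every two weeks to week 14, and Section 10.2.2 provides for temporary suspension and reinstitution.

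**Conclusion.** The concern holds as a defect in the wording of the causality scale. A plausibly timed event of a new kind has no related category that fits it, and absence of a known pattern is a positive match only for not related.

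The consequences are limited. The related-AE tables are directly exposed, since no second causality assessor is stated for non-serious events. The investigator's route to SUSAR causality is weakened, with the sponsor's route intact. For completers, at most about two weeks of follow-up on non-serious events is at stake. The secondary endpoint and the all-AE, SAE and severity tables do not depend on causality.

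A reader might also conclude that the related-AE comparison is biased in favour of LEO 138559. The direction is plausible, but neither its presence nor its size can be established from the documents. It depends on how literally the blinded investigator applies the list, and on what the investigator's brochure, which is not among the documents, treats as a known response. The percentages above show only that a first-time reaction is realistic; they do not measure bias.

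**What to change.** Amend Appendix 2 and carry the same wording into the AE and SAE form guidance:

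1. Remove absence of a known pattern from the marks of not related. The minimum alternative is a sentence stating that absence of a known pattern is not by itself grounds for not related.
2. Let possibly related apply where the timing is reasonable and a causal role of the trial product cannot be ruled out, whether or not a pattern is known.
3. Keep known pattern as a supporting feature for probably related only.
4. State that the marks are guidance and need not all be met.

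The cost is amendment text and form guidance. No endpoint, sample size or analysis changes. The downside is that somewhat more AEs will be classed as possibly related in both arms, so the related-AE tables become a little less specific.

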#### **Outcome**

The *outcome* of the event according to the investigator's clinical judgement should be classified using the categories below.

Fatal	The subject has died as a consequence of the event. Date of death is recorded as stop date for the AE.	
Not recovered/ not resolved	Event is still ongoing.	
Recovering/ resolving	The subject is clearly recovering from an event. The event is not yet completely resolved.	
Recovered/ resolved	The event has stopped. The stop date of the event must be recorded.	
Recovered/ resolved with sequelae	The event has reached a state where no further changes are expected and the residual symptoms are assumed to persist. An example is hemiparesis after stroke.	
	The stop date of the event must be recorded. In case of an SAE, the sequelae should be specified.	
Unknown	Unknown to investigator, e.g. subject lost to follow-up.	

#### LEO Pharma definitions versus CDISC definitions

Note that as per the above definition, LEO Pharma uses 'recovered/resolved' only if an event has actually stopped. According to the CDISC definition, the category 'recovered/resolved' also includes events which have improved. However, following the LEO Pharma definitions above, such an improved event will instead be classified as 'not recovered/not resolved' or 'recovering/resolving'.

Similarly, it should be noted that as per the above definition, LEO Pharma uses 'recovered/resolved with sequelae' only if an event has reached a state where the residual symptoms are assumed to persist. According to CDISC, an event is considered 'with sequelae', if it has 'retained pathological conditions'. Consequently, it is likely that some of the events classified by LEO Pharma with the outcome 'recovered/resolved with sequelae' could have been classified with the outcome 'recovered/resolved' according to the CDISC definition.

In summary, the definitions used by LEO Pharma are more conservative than those used by CDISC.

### **Appendix 3: Trial governance considerations**

#### Appendix 3A: Regulatory and ethical considerations

This trial will be conducted in accordance with the protocol and with the following:

- Consensus ethical principles derived from international guidelines including the current version of the Declaration of Helsinki [37] and Council for International Organizations of Medical Sciences (CIOMS) International Ethical Guidelines [58].
- Current version of applicable International Council for Harmonisation Good Clinical Practice (ICH GCP) Guidelines [55].
- EU General Data Protection Regulation 2016/679 of 27 April 2016.
- Applicable laws and regulations.

The appropriate regulatory authority(ies) must be notified of/approve the clinical trial as required.

Any documents that the IRB/IEC may need to fulfil its responsibilities (such as the trial protocol, protocol amendments, investigator's brochure [as applicable], subject information sheet, and informed consent form(s), or advertisements) will be submitted to the IRB/IEC. These documents must be reviewed and approved by the IRB/IEC before the trial is initiated.

Any amendments to the protocol must be approved by/receive favourable opinion from relevant regulatory authorities and IRBs/IECs, as required, prior to implementation.

The principal investigator will be responsible for the following, if required by local legislation:

- Providing written summaries of the status of the trial to the IRB/IEC annually or more frequently in accordance with the requirements, policies, and procedures established by the IRB/IEC.
- Notifying the local IRB/IEC of SAEs or other significant safety findings as required by IRB/IEC procedures.
- Providing oversight of the conduct of the trial at the trial site and ensuring adherence to applicable national and international legislation.

#### **Appendix 3B: Informed consent process**

Subjects will receive written and verbal information concerning the clinical trial. This information will emphasise that participation in the clinical trial is voluntary and that the subject may withdraw from the clinical trial at any time and for any reason. All subjects will be given an opportunity to ask questions and will be given sufficient time to consider before consenting.

The subject's signed and dated informed consent to participate in the clinical trial will be obtained prior to any clinical trial-related procedure being carried out in accordance with ICH GCP and all applicable laws and regulations. The authorised person obtaining the informed consent must also sign the ICF.

Subjects will be re-consented to the most current version of the ICF(s) during their participation in the trial, if required.

A copy of the ICF(s) must be provided to the subject.

